1.1 Study design

This is a randomized, phase III, double blind, placebo controlled, international study to determine the efficacy and safety of treatment with fulvestrant with ribociclib versus fulvestrant with placebo in men and postmenopausal women with HR+, HER2-negative advanced breast cancer. This study will consist of 4 phases: screening (up to 28 days), randomized treatment, post-treatment efficacy follow-up, and post-treatment survival follow-up.

Approximately 660 patients will be randomly assigned to one of the following treatment arms in a 2:1 ratio.

- Experimental arm: fulvestrant (500 mg intramuscular [as two 5 mL injections] on Cycle 1 Days 1 and 15 (C1D1 and C1D15), and on CnD1 thereafter) + ribociclib (600 mg by mouth once daily for three weeks followed by one week break, in a 28-day cycle)
OR
- Control arm: fulvestrant (500 mg intramuscular [as two 5 mL injections] on Cycle 1 Days 1 and 15 (C1D1 and C1D15), and on CnD1 thereafter) + ribociclib placebo (by mouth once daily for three weeks followed by one week break, in a 28-day cycle)

Randomization will be stratified by the following factors:

1. Lung or liver metastases: (yes vs no)
2. Previous endocrine therapy (A vs B) according to the following definition:

A) Patients treatment naïve in the metastatic/advanced disease setting:

- i- whose disease relapsed >12 months after completion of (neo)adjuvant endocrine therapy with no subsequent treatment for advanced/metastatic disease,

OR

- ii- with de-novo advanced/metastatic disease (no prior exposure to endocrine therapy).

- B) Patients who received up to 1 line of treatment for metastatic/advanced disease:
- i- whose disease relapsed on or within 12 months from completion of (neo) adjuvant endocrine therapy, with no subsequent treatment for advanced/metastatic disease,
OR
 - ii- whose disease relapsed > 12 months from completion of (neo) adjuvant endocrine therapy, and progressed on or after subsequent endocrine treatment for advanced/metastatic disease,
OR
 - iii- with advanced/metastatic disease at the time of diagnosis that progressed on or after endocrine therapy for advanced/metastatic disease with no prior (neo) adjuvant treatment for early disease.

[figure not shown]
PFS, as assessed by the local radiologists/investigators and using RECIST 1.1 criteria will be the primary endpoint. PFS as assessed through audit-based blinded independent review committee (BIRC) will be a supporting end point for primary analysis.

An Independent Data Monitoring Committee (IDMC) will be constituted and will monitor safety and efficacy data. A Steering Committee (SC) will be established comprised of investigators and Novartis personnel participating in the trial to ensure transparent management of the study according to the protocol.

Overall survival is a secondary endpoint in this study and will be tested provided the primary endpoint PFS is statistically significant. A Lan-DeMets alpha spending function with O'Brien Fleming type stopping boundary (as implemented in East 6.3) will be used to maintain the overall type-I error rate for OS. The interim OS analyses will be performed by Novartis. Further details regarding the group sequential design are provided in [Section 3.14](#).

The study design is summarized in [Figure 1-1](#).

Figure 1-1 Study Design

1.2 Objectives

The study objectives and corresponding endpoints as specified in the protocol are provided in [Table 1-1](#).

Table 1-1 Study objectives

Objective	Endpoint	Analysis
Primary		
To compare PFS between ribociclib in combination with fulvestrant to placebo in combination with fulvestrant among men and postmenopausal women with HR+, HER2-negative advanced breast cancer who received no or only one prior endocrine treatment for advanced disease	PFS based on local radiology assessments and using RECIST 1.1 criteria	Refer to Section 3.8.1
Secondary		
To compare the two treatment arms with respect to overall survival.	Overall survival	Refer to section 3.8
To evaluate the two treatment arms with respect to overall response rate, clinical benefit rate, time to response and duration of response.	ORR as defined by RECIST 1.1. CBR, defined as percentage of patients with CR, PR or SD lasting 24 weeks or longer, TTR, DOR per RECIST 1.1	Refer to section 3.8

Objective	Endpoint	Analysis
To evaluate the two treatment arms with respect to time to deterioration of ECOG performance status.	Time to definitive deterioration of ECOG performance status from baseline	Refer to section 3.8
To evaluate the safety and tolerability of ribociclib in combination with fulvestrant.	Frequency/severity of AEs, laboratory abnormalities	Refer to section 3.9
To evaluate patient reported outcomes for health-related quality of life in the two treatment arms.	Time to 10% deterioration in the global health status/QOL scale score of the EORTC QLQ-C30 Change from baseline in the global health status/QOL scale score of the EORTC QLQ-C30	Refer to section 3.8
To characterize the pharmacokinetics (PK) of ribociclib (and relevant metabolites such as LEQ803) when given in combination with fulvestrant.	Concentration by time point for ribociclib (and relevant metabolites such as LEQ803)	Refer to section 3.10

2 Definitions and general methodology

2.1 Definitions

2.1.1 Study drug and study treatment

Study drug is defined as ribociclib or matching placebo.

Study treatment is defined as ribociclib + fulvestrant, or matching placebo + fulvestrant.

2.1.2 Date of first administration of study drug

The date of first administration of study drug is defined as the first date when a nonzero dose of study drug is administered and recorded on the dose administration DAR CRF. The date of first administration of study drug will also be referred to as start of study drug. Similar definitions apply for the other components of study treatment.

2.1.3 Date of last administration of study drug

The date of last administration of study drug is defined as the last date when a nonzero dose of study drug is administered and recorded on the DAR CRF. Similar definitions apply for the other components of study treatment.

2.1.4 Date of first administration of study treatment

The date of first administration of study treatment is defined as the first date when a nonzero dose of any component of study treatment is administered and recorded on the DAR CRF. The date of first administration of study treatment will also be referred to as the start of study treatment.

2.1.5 Date of last administration of study treatment

The date of last administration of study treatment is defined as the last date when a nonzero dose of any component of study treatment was administered and recorded on the DAR CRF.

2.1.6 Study day

The study day will be calculated as:

- The date of the event (visit date, onset date of an event, assessment date etc.) – reference start date + 1 if event is on or after the reference start date;
- The date of the event (visit date, onset date of an event, assessment date etc.) – reference start date if event precedes the reference start date.

The reference start date for safety assessments (e.g. adverse event onset, laboratory abnormality occurrence, vital sign measurement, dose interruption etc.) is the start of study treatment. (Note: if an adverse event starts before the start of study treatment the study day displayed on the listing will be negative).

The reference start date for all other, non-safety assessments (e.g., tumor assessment, death, disease progression, tumor response, ECOG performance status, and patient reported outcomes (PRO)) is the date of randomization. In other words, all efficacy time-to-event variables (e.g. progression-free survival, overall survival, time to response) will be calculated from date of randomization. (Example: if randomization date is 15DEC2014, start of study drug is on 18DEC2014, and the date of death is 28DEC2014 then the study day when the death occurred is 14).

The study day will be displayed in data listings.

2.1.7 Baseline

For efficacy evaluations, the last available assessment on or before the date of randomization will be used as the “baseline” value or “baseline” assessment. In the context of baseline definition, the efficacy evaluations also include ECOG performance status and patient-reported outcomes. For RECIST based endpoints including PFS and response rates, a window of 7 days from the start of study treatment will be allowed, i.e. the investigator/BIRC-reported responses will be maintained and baseline considered valid if the baseline assessment is within 7 days of treatment start date.

For safety evaluations (e.g. laboratory assessments and ECG), the last available assessment before or at date of start of study treatment will be used as the ‘baseline’ assessment. Assessments specified to be collected post-dose on the first date of treatment are not considered as baseline values.

If patients have no value as defined above, the baseline results will be considered missing.

2.1.8 On-treatment assessment/event

Safety summaries and selected summaries of deaths will summarize only on-treatment assessments/events. An on-treatment assessment/event is defined as any assessment/event in the following time interval:

[date of first administration of study treatment, date of last administration of study treatment + 30 days], i.e. including the lower and upper limits. (Note: However, the calculation of study treatment duration will use different rules as specified in [Section 3.6.1](#)).

An AE started in the screening phase and ongoing in the on-treatment phase will not be considered as an on-treatment AE unless it has worsened.

If the last date of study treatment is missing, any assessment/event occurring after the start of study treatment will be considered as on-treatment.

Data listings will include all assessments/events, flagging those which are not on-treatment.

Note: The date of first administration of study treatment and the date of last administration of study treatment are defined in [Sections 2.1.4](#) and [2.1.5](#), respectively.

2.1.9 Last contact date

For patients not known to have died at the analysis cut-off, the last contact date will be derived using the last complete date among the following:

Table 2-1 Last contact date data sources

Source data	Conditions
Date of Randomization	No Condition
Last date patient was known to be alive from Survival Follow-up page	Patient status is reported to be alive, lost to follow-up or unknown.
Start/End dates from further antineoplastic	Non-missing medication/procedure term.

Source data therapy	Conditions
Start/End dates from drug administration record	Non-missing dose. Doses of 0 are allowed.
Date of discontinuation/study phase completion from end of treatment disposition page	No condition.
Date of discontinuation/Study phase completion from end of post treatment follow up phase disposition page	No condition
Date of ECG assessment	At least 1 non-missing parameter value
Date of PRO assessment	At least 1 non-missing answer to questionnaire
Tumor (RECIST) assessment date	For non-target lesion: non-missing lesion status For target lesion: non-missing lesion diameter For new lesion: "Is there a new lesion?" yes
Laboratory sample collection date	At least 1 non-missing parameter value
PK collection dates	At least 1 non-missing PK concentration
Vital signs date	At least one non-missing parameter value
Concomitant medication date	At least one non-missing name of medication
████████████████████	████████████████████
Body fluid/Tissue Collection date	Non-missing result (positive/negative tumor cells)
Hospitalization admission/discharge date	Non-missing type of facility admitted to
Cardiac imaging date	Non-missing LVEF or overall interpretation
Performance Status date	Non-missing performance status
Start/End dates of AE	Non-missing verbatim term

The last contact date is defined as the latest complete date from the above list on or before the data cut-off date. The cut-off date will not be used for last contact date, unless the patient was seen or contacted on that date. No dates post cut-off date will be used. Completely imputed dates (e.g. the analysis cut-off date programmatically imputed to replace the missing end date of a dose administration record) will not be used to derive the last contact date. Partial date imputation is allowed for event (death)/censoring coming from 'Survival information' eCRF.

The last contact date will be used for censoring of patients in the analysis of overall survival.

2.2 Data included in the analysis

The primary PFS analysis will be carried out after approximately 364 events have been documented based on local investigator assessment. Up to 3 analyses for OS may be performed as described in section 3.8. For each of the analysis time points, statistical analyses will be performed using all data collected in the database up to the data cutoff date. Any data

collected beyond the cutoff date will not be included in the analysis and will not be used for any derivations.

2.3 Analysis sets

2.3.1 Full analysis set (FAS)

The Full Analysis Set (FAS) consists of all randomized patients. Following the intent-to-treat principle, patients will be analyzed according to the treatment and stratum they were assigned to at randomization. The FAS will be the primary analysis set for efficacy analyses.

2.3.2 Safety set

The Safety Set consists of all patients who received at least one dose of any component of study treatment and have at least one post-baseline safety assessment. Patients will be analyzed according to the treatment actually received. Treatment actually received refers to the treatment the patient was randomized to, unless the alternative treatment was received throughout the trial. If a patient takes at least one dose of the randomized treatment then the treatment actually received is the randomized treatment. The statement that a patient has no AE constitutes a safety assessment. Occurrence of a death constitutes a safety assessment as well.

2.3.3 Per protocol set

The Per-Protocol Set (PPS) includes the subset of the patients in the FAS without major protocol deviations, and who took at least one dose of study treatment. Patients with any of the following protocol deviations will be excluded from the PPS.

- Written informed consent not obtained;
- Patient is not post-menopausal;
- Patient without HR+ and HER2- advanced breast cancer at baseline;
- Patient received prior fulvestrant treatment;
- Patient received prior CDK4/6 inhibitor;
- Patient with recurrence on or within 12 month of adjuvant therapy and subsequent advanced treatment.
- Baseline ECOG performance status >1;
- Neither measurable disease nor predominantly lytic bone lesion at baseline;
- Patient received more than 1 line of prior hormonal anti-cancer therapy for advanced breast cancer;
- Patient received prior chemotherapy for advanced breast cancer;
- Patient received different treatment throughout the study than the one randomized to.

A sensitivity analysis of the primary endpoint (i.e., PFS) will be performed using PPS if the primary efficacy analysis is significant and the FAS and PPS differ.

2.3.4 Pharmacokinetic analysis set

The Pharmacokinetic analysis set (PAS) consists of all patients who provide at least one evaluable PK concentration (see [Section 3.10.1](#) for definition of evaluable PK concentration).

2.3.5 Patient classification

Patients may be excluded from the analysis sets defined above based on the protocol deviations entered in the database and/or on specific subject classification rules as defined in [Table 2-1](#).

Table 2-1 Patient classification based on protocol deviations and non-protocol deviation criteria

Analysis set	Protocol deviations leading to exclusion	Non-protocol deviation criteria leading to exclusion
FAS	No written informed consent	NA
Safety set	No written informed consent	No post-baseline safety assessment or no dose of study treatment
Per Protocol set	Any major protocol deviation as listed in definition of per protocol set	No dose of study treatment.

Withdrawal of Informed Consent

Any data collected in the clinical database after a subject withdraws informed consent from all further participation in the trial, will not be included in the analysis data sets. The date on which a patient withdraws full consent is recorded in the eCRF.

Death events may be used in the analysis if captured from public records (registers), local law and patient informed consent permitting.

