### 10.5.1 Overall Survival

One of the secondary objectives of the study is to determine whether treatment with fulvestrant + ribociclib prolongs overall survival (OS) compared to treatment with fulvestrant + placebo.

OS is defined as the time from date of randomization to date of death due to any cause. If a patient is not known to have died, then OS will be censored at the date of last known date patient alive.

Assuming proportional hazards model for OS, the following statistical hypothesis for OS will be tested using a stratified log-rank test (stratified according to randomization stratification factors) at the one-sided 2.5% level of significance:

$H_0: \theta_2 \geq 0$  vs.  $H_a: \theta_2 < 0$

where  $\theta_2$  is the log-hazard ratio (fulvestrant+ribociclib arm vs. fulvestrant+placebo arm) of OS.

The analyses for OS will be based on the FAS. The distribution of OS will be compared between the two treatment groups using a stratified log-rank test at one-sided 2.5% level of significance.

[figure not shown]
The final OS analysis will not be performed at the time point of the final PFS analysis, but after additional follow-up. Therefore, a four-look design is considered for OS.

1. OS will be hierarchically tested (provided the primary PFS analysis is statistically significant) in the following way. The first potential time point for OS analysis will be at the time of the primary PFS analysis at which time approximately 161 deaths are expected. If PFS is statistically significant at this stage, OS will also be tested. If OS is not statistically significant at this stage, the 2nd OS analysis is planned after approximately 263 deaths are expected. If OS is not statistically significant at this stage, the final OS analysis will be planned after approximately 351 deaths.

The type I error probability for OS tests will be controlled by using a separate Lan-DeMets (O'Brien-Fleming) alpha spending function independent of the one used for the primary efficacy analysis of PFS at the one-sided type I error of  $\alpha=0.025$ . This guarantees the protection of the overall level  $\alpha = 2.5\%$  across the two hypotheses and the repeated testing of the OS hypotheses in the interim and the final analyses ([Glimm 2010](#)).

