3.8.2.1 Overall survival

Comparing the overall survival (OS) between ribociclib +fulvestrant and placebo+fulvestrant is a secondary objective in this study. OS is defined as the time from date of randomization to date of death due to any cause. If a patient is not known to have died at the time of analysis

cut-off, then OS will be censored at the date of last contact. Assuming proportional hazards for OS, the following statistical hypotheses will be tested:

$$H_{02}: \theta_2 \geq 0 \text{ vs. } H_{A2}: \theta_2 < 0$$

Where θ_2 is the log OS hazard ratio (fulvestrant+ ribociclib arm vs. fulvestrant + placebo arm). The analysis to test this hypothesis is a stratified log-rank test at an overall one-sided 2.5% level of significance. The stratification will be based on the randomization stratification factors.

A maximum of 3 analyses are planned for OS: at the time of the analysis for PFS (provided PFS is significant), at which point a total 161 deaths (46% of OS events) are expected, after 263 events (75% of OS events) have been documented, and a final analysis for OS when 351 deaths (100% of OS events) are expected (expected 56 months from date of first patient to be randomized).

OS tests will be carried out using a Lan-Demets (O'Brien-Fleming) alpha spending function. OS will only be tested if the primary efficacy analysis has been shown to be statistically significant. Analyses will be based on the FAS population according to the randomized treatment group and strata assigned at randomization. All deaths recorded up to the cut-off date will be included in the analysis. The survival distribution of OS will be estimated using the Kaplan-Meier method, and Kaplan-Meier curves, medians and 95% confidence intervals of the medians intervals along with the proportion of patients alive at 6 month interval starting from 12 month will be presented for each treatment group. The hazard ratio for OS will be calculated, along with its 95% confidence interval, using a stratified Cox model using the same stratification factors as the log-rank test.

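### Register deaths after consent withdrawal may be counted for OS with no matching rule for patients found alive, so OS censoring depends on outcome wherever that permission is used

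*SAP*

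**What the plan says.** The rule is in the SAP for the primary PFS analysis, which also governs the OS tests. Section 2.3.5 states that data collected "after a subject withdraws informed consent from all further participation in the trial, will not be included in the analysis data sets". It then adds the exception: "Death events may be used in the analysis if captured from public records (registers), local law and patient informed consent permitting".

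Section 2.1.9 fixes the censoring date: "The last contact date will be used for censoring of patients in the analysis of overall survival". Among the readable rows of its source table (one row is blacked out), the only direct vital-status source is "Last date patient was known to be alive from Survival Follow-up page"; the rest are trial records such as visits, laboratory samples and scans. The section adds: "The cut-off date will not be used for last contact date, unless the patient was seen or contacted on that date". Section 3.8.2.1 says of OS: "All deaths recorded up to the cut-off date will be included in the analysis".

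Protocol 7.1.7 ends survival follow-up at withdrawal of consent. Protocol 7.1.4 defines withdrawal as including refusal of any further collection of personal data. Protocol 10.5.1 says: "If a patient is not known to have died, then OS will be censored at the date of last known date patient alive".

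**The concern.** Take two patients who both withdraw at month 10 and are both looked up in a register at a month-56 cut-off. The one who died at month 40 is an OS event at month 40, with 40 − 10 = 30 further months in the risk set. The one found alive has no source that carries a later date and is censored at or before month 10. The same look-up extends follow-up for one and not for the other, and the only difference is the outcome. Censoring is then informative because of the rule itself, even if withdrawal has nothing to do with prognosis.

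OS is the secondary endpoint with hierarchical testing and its own alpha-spending function. If the arms withdraw at different rates, the distortion does not cancel in the hazard ratio, and the 2.5% one-sided level is no longer assured.

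**Working it through.** **1. The plan's OS design reproduces.** SAP 3.17 and 3.8.2.1 give hazard ratio 0.71, one-sided 2.5%, 85% power, 2:1 allocation and looks at 161, 263 and 351 deaths.
- Fixed-design deaths: (1.960 + 1.036)² / [(2/3)(1/3)(ln 0.71)²] = 8.978 / (0.2222 × 0.1173) = 344.4, so 345. The group-sequential 351 is consistent with this.
- Spending function in SAP 4.3.1: cumulative alpha 0.0009 at 161/351 = 0.459, 0.0096 at 263/351 = 0.749, and 0.025 at the end. The Z boundaries are 3.110, 2.353 and 2.013.
- Cumulative power is 14.4%, 60.7% and 85.0%, against the plan's 14%, 60% and 85%.

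**2. Why OS is shortened.** Take withdrawn control patients with the plan's 30-month median (hazard ln 2/30 = 0.0231 per month), all register-covered. As an illustration, give each 36 months between withdrawal and cut-off.
- Share dying after withdrawal: 1 − exp(−0.0231 × 36) = 0.565.
- True person-time per patient: 0.565/0.0231 = 24.4 months.
- Survivors' share, which the rule discards: 0.435 × 36 = 15.7 months.
- Apparent post-withdrawal hazard: 0.565/(24.4 − 15.7) = 0.065 per month, about 2.8 times the true 0.0231.

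Every death is kept and the survivors' time at risk is lost, so each withdrawn patient adds excess hazard to the arm they belong to.

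**3. Simulated size.** Inputs from the plan: 660 patients 2:1, 19-month uniform accrual, control median 30 months. Assumed: exponential survival; withdrawal unrelated to prognosis; the withdrawal percentage is the share withdrawing before death and before month 56. The percentages are illustrative: SAP 3.17 gives only 10% dropout overall, not split by arm or type of loss.

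One-sided error with true hazard ratio 1, at the planned looks and boundaries. Ranges cover separate runs, the larger with 25,000 trials per row:

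| Withdrawal, control / ribociclib | Register coverage | Error |
|---|---|---|
| 10% / 10% | full | 2.6 to 2.8% |
| 12% / 9% | half | 2.9 to 3.1% |
| 12% / 9% | full | 3.5% |
| 14% / 8% | full | 4.5 to 4.6% |
| 18% / 6% | half | 4.4% |
| 18% / 6% | full | 6.6 to 7.0% |
| 6% / 18% | full | 0.8% |

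At 18% / 6%, censoring everyone at withdrawal gives 2.4%, and using register status both ways gives 2.6%.

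**4. Effect on the estimates, true hazard ratio 0.71, full coverage, month-56 cut-off.**
- 10% / 10%: medians fall from 30.0 to about 29.1 months (control) and from 42.3 to 40.3 months (ribociclib); the hazard ratio stays at 0.71.
- 14% / 8%: hazard ratio reads 0.69. 18% / 6%: 0.67.
- 6% / 18%: hazard ratio reads 0.75, and three-look power is about 74%, against about 86% under the symmetric rule.

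**5. Sensitivity to the definition.** If the percentages mean cumulative withdrawal ignoring death, 18% / 6% at full coverage gives about 5% error under the planned design.

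**The case against.** The permission is conditional. The SAP says register deaths may be used, and only where law and consent allow. Since Protocol 7.1.4 defines withdrawal as refusing further collection of personal data, look-ups after full withdrawal could be few. This stands: full coverage is a ceiling, and a reader who infers that the SAP always counts these deaths goes further than its text. It does not remove the asymmetry where the permission is used, and it leaves inclusion of events to discretion.

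A reader might also infer that the SAP departs from Protocol 10.5.1, which censors at the last date known alive. The documents do not support that. Protocol Appendix 2 (14.2.26) takes last contact from visits, laboratory samples, tumor assessments or the survival follow-up page. Survival follow-up stops at withdrawal. Nothing makes a register check a known-alive date, and absence from a death register is not a record of being alive.

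A single test at a fixed month-56 cut-off gives a larger error, about 9% at 18% versus 6%. That is not the planned test: under the null it uses about 433 deaths rather than 351 and ignores the earlier looks. Nor does anything in the documents point to a threefold imbalance in a double-blind trial.

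Finally, OS was met at the second interim analysis and Protocol 10.5.1 plans no further formal test. This stands and shapes the remedy. The final-report SAP omits the register sentence but plans no OS comparison, so it does not settle how the tested OS data were handled.

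**Conclusion.** The point holds as a defect in the rule. Where register deaths are used after withdrawal, OS follow-up depends on outcome: both OS curves are pulled down, and with unequal withdrawal the hazard ratio moves against the arm with more withdrawals. More placebo withdrawal favors ribociclib; more ribociclib withdrawal makes the test conservative.

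The size cannot be fixed from the documents, because withdrawal by arm and register coverage are not given. With equal withdrawal the test is essentially unaffected, and with modest imbalance the inflation is small. Only a marked imbalance with high coverage takes the error to 6.6 to 7.0%.

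A reader might conclude that the reported OS significance is unsafe. The documents do not show that: they give no count of register deaths and no withdrawal split. Through the second look, where OS was met, simulated cumulative error at 18% versus 6% was about 1.7 to 2.3%, against about 1.2% with equal withdrawal. The readable text contains no sensitivity analysis that would settle the matter.

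**What to change.** Make the rule symmetric in SAP 2.3.5. Where law and consent permit a register check after withdrawal, use vital status either way: deaths are events, and patients confirmed alive are censored at the register check date or the data cut-off, whichever is earlier. Add the register check date to the last-contact sources in Table 2-1. Where only deaths can be obtained, censor OS at the last contact on or before withdrawal and do not count later register deaths.

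Because formal OS testing is complete, also report withdrawals of consent and register deaths by arm, and re-run OS with every withdrawn patient censored at withdrawal as a sensitivity analysis.

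The cost is a few sentences, one table row and one extra analysis. The downside is that a few register deaths may drop out of the OS count. If sicker patients are the ones who withdraw, censoring at withdrawal has a bias of its own, so the two-way rule is preferable wherever it can be applied.
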